Comparative Effects of Blood Flow Restriction and Traditional Strength Training on Proximal Shoulder Musculature: A Randomized Clinical Trial

Approved by the ethics committee of Instituto Politécnico de Saúde do Norte (31/CE-IPSN/2024).

April 2024

STUDY OBJECTIVES

This study compared a 4-week blood-flow-restriction (BFR) resistance-training program performed at 30% of one-repetition maximum (1RM) with traditional high-load strength training at 70% of 1RM on shoulder muscle strength, power, endurance, and hypertrophy in healthy adults.

STUDY DESIGN

Parallel-group randomized controlled trial with two intervention arms: an experimental BFR group ($n = 12$; 3 men, 9 women) and an active comparator high-load group ($n = 11$; 3 men, 8 women; one dropout). All participants provided written informed consent in accordance with the Declaration of Helsinki.

PARTICIPANTS AND RECRUITMENT

Healthy volunteers were recruited via social media, discussion groups, and physical postings at CESPU facilities. Individuals of both sexes were eligible because prior work indicates comparable metabolic responses to BFR across genders. Eligibility was screened using an online questionnaire covering demographics, sport participation, and medical history. Eligible respondents were contacted by email to schedule baseline testing.

Eligibility Criteria

Inclusion criteria

- Age 18–40 years
- Body mass index (BMI) 18.5–30 kg/m² (individuals with obesity are commonly excluded due to higher cardiovascular, respiratory, and rheumatologic risk)

Exclusion criteria

- Participation in sports that heavily use the dominant arm (e.g., tennis, volleyball, handball)
- Current upper-limb strength training
- History of trauma or surgery involving the dominant upper limb

- Acute or chronic shoulder pain or radiating pain
- Cervical disc herniation or prior cervical surgery
- Upper-limb edema
- History of deep-vein thrombosis or oncologic/metabolic disease
- Pregnancy
- Persistent symptoms during training: numbness, tingling, or pain >7/10 on a numeric rating scale (BFR group criterion)
- Missing more than one training session

Randomization was performed with Sealed Envelope™.

METHODS

Before data collection, the research team completed a familiarization phase to standardize equipment use, test administration, training procedures, and safety protocols. Responsibilities were assigned to specific team members, and minor adjustments were implemented as needed to ensure consistency and measurement accuracy.

Outcome assessments were performed after a standardized warm-up and always in the same sequence: Arm Circumference, Single-Arm Seated Shot-Put Test, Vertical Lift Strength, and Shoulder Endurance Test. Measurements were obtained at baseline (M0) and at least 24 h after the final training session (M1). Participants were instructed to avoid strenuous upper-limb activity for 24 h before testing.

Data-Collection Procedures

Arm Circumference: Circumference at the axillary level of the dominant arm was used as a proxy for deltoid muscle mass. With the participant at rest, three measurements were taken using a standard tape; the mean value was analyzed.

Single-Arm Seated Shot-Put Test (SASSPT): To assess shoulder power and upper-limb function, participants sat with trunk and shoulders against a wall, lower limbs extended, and the non-tested arm resting on the ipsilateral thigh to minimize compensation. Using a 4-kg medicine ball, participants performed maximal throws. Distances were recorded using floor tape; throws were video recorded to confirm first contact points. Three trials were performed; the mean distance was analyzed.

Vertical Lift Strength. Isometric strength for a vertical-lift task was measured with the Smart Groin Trainer (NeuroExcellence, Braga, Portugal). Participants were seated with the shoulder at 60° abduction and the elbow flexed; force was applied in the direction of vertical arm elevation. Three trials were performed; the best value was analyzed.

Shoulder Endurance. The Shoulder Endurance Test (SET) was used for its controlled cadence. Participants stood with their back against a wall, the contralateral heel touching the wall, and the ipsilateral leg positioned forward. The movement consisted of shoulder abduction to 90° with external rotation to 90° while touching the wall. Resistance was provided by a red elastic band; the hand-to-anchor distance was fixed at 1 m. A metronome guided cadence, starting at 60 bpm and increasing by 30 bpm every 20 s up to 150 bpm. The test ended when cadence or movement quality could not be maintained. Time to termination (seconds) was recorded.

Training Protocol

The intervention lasted 4 weeks with two sessions per week. Each session began with a warm-up including shoulder and upper-limb mobility and stretching. During the first session, 1RM for each exercise was estimated using a repetition-to-failure approach with appropriate coefficients.

Three shoulder-focused exercises were prescribed:

- Standing shoulder abduction to 90°, then return to start.
- Seated dumbbell overhead press with back support (from shoulder level to full overhead and return).
- External rotation performed lying on a bench with the upper arm against the torso and the elbow flexed at 90°.

High-load strength training group: Training followed ACSM hypertrophy guidelines at 70% 1RM. For each exercise, participants completed four sets of 8–10 repetitions with 2-min rests between sets and exercises. Tempo was moderate (1 s concentric, 2 s eccentric).

Low-load strength training with BFR group: Exercises were performed at 30% 1RM. Each exercise totaled 75 repetitions across four sets (30/15/15/15) with 30-s inter set rests. Tempo was 2 s concentric and 2 s eccentric.

BFR Application

BFR was delivered using SmartCuffs® 3.0 PRO (Smart Tools Plus). At each session start, the device determined arterial occlusion pressure, and cuffs were set to 50% limb occlusion pressure. With participants seated, a 7-cm cuff was placed directly on the skin (or over a thin T-shirt) at the most proximal portion of the dominant arm (just distal to the deltoid insertion). Pressure was maintained during each exercise, released for 60 s between exercises, and reapplied for the next exercise. Participants rated pain, tingling, and numbness on a 0–10 numeric rating scale; symptoms >7/10 prompted protocol adjustment or session cancellation.

Each training session lasted approximately 45 minutes in both groups. Participants were asked to maintain their usual physical-activity levels throughout the study.

STATISTICAL ANALYSIS

Analyses were performed in SPSS version 29.0 (SPSS Inc., Chicago, IL, USA). Quantitative variables are presented as mean \pm SD or median (interquartile range), as appropriate. Between-group comparisons used Fisher's exact test, the Mann-Whitney U test, or independent-samples t tests. Within-group pre- to post-changes were evaluated with paired-samples t tests. For significant outcomes, Cohen's d was calculated and interpreted as: very small, $0.01 < d \leq 0.20$; small, $0.20 < d \leq 0.50$; moderate, $0.50 < d \leq 0.80$; large, $0.80 < d \leq 1.20$; very large, $1.20 < d \leq 2.00$; and huge, $d > 2.00$. Statistical significance was set at $p < 0.05$.

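### The between-group tests use neither the M0 value nor sex, although both are recorded; adjusting for M0 would recover most of any lost precision, and sex is an inexpensive extra covariate

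*Combined protocol and SAP*

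**What the plan says.** The Study Design section gives a BFR arm of 12 (3 men, 9 women) and a high-load arm of 11 ("3 men, 8 women; one dropout"). Participants and Recruitment explains why both sexes could enrol: "prior work indicates comparable metabolic responses to BFR across genders".

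The four outcomes in Data-Collection Procedures are absolute quantities: arm girth, throw distance, isometric lifting force, and seconds on the endurance test. No scaling to body size is stated, and the test resistance is common to everyone. For the throw: "Using a 4-kg medicine ball, participants performed maximal throws". The endurance test likewise uses one type of elastic band at one fixed distance. Each outcome is measured at baseline (M0) and after training (M1).

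The Statistical Analysis section states: "Between-group comparisons used Fisher's exact test, the Mann-Whitney U test, or independent-samples t tests". Within-arm change is tested with paired t tests. No covariate, stratum or baseline adjustment is mentioned, and the variable compared between arms (M1 or change from M0) is not named. The documents give no SD, sex difference, pre-post correlation or power calculation.

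**The concern.** When two groups of people differ in the level of an outcome and are pooled, the difference between them enters the error term of an unadjusted comparison. Similar metabolic response to BFR bears on whether the treatment works alike in men and women. It does not bear on whether they throw equally far or lift equally hard.

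Training loads are percentages of each person's own 1RM, so larger absolute gains in stronger people are also possible, though the documents do not show this.

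With 23 participants, avoidable variance can decide whether the comparison is informative. Two recorded variables could remove some of it: the M0 value, which carries each person's own level, and sex. The plan uses neither between arms. Because it does not name the analysed variable, the least efficient option, an unadjusted comparison of M1, remains open.

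**Working it through.** **Inputs from the documents.** 12 vs 11 participants, taken as the numbers analysed; 3 men per arm; significance level 0.05, taken as two-sided.

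**Assumptions, varied because the documents give no values.** D is the male-female difference in within-sex SDs; r is the within-sex M0-M1 correlation; men may gain up to 0.5 SD more than women; the true group difference is 0.6 within-sex SD. There is no power figure in the plan to reproduce.

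**1. Balance.** Men make up 3/12 = 25.0% and 3/11 = 27.3%, a difference of 2.3 percentage points. Sex therefore moves an unadjusted M1 contrast by only 0.0227 × D, or 0.045 SD at D = 2. The issue is precision; confounding is minor.

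**2. Error term if M1 is compared.** The within-arm variance of the male indicator is [12 × 0.25 × 0.75 + 11 × (3/11) × (8/11)] / 21 = (2.250 + 2.182) / 21 = 0.211. The residual variance is 1 + 0.211 D², and SE = √[variance × (1/12 + 1/11)].

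| D | Variance | SE, group only | SE, group + sex |
|---|---|---|---|
| 1 | 1.21 | 0.459 | 0.418 |
| 2 | 1.84 | 0.567 | 0.418 |
| 3 | 2.90 | 0.711 | 0.418 |

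**3. Hand check of power at D = 2.** Significance needs a difference of 2.080 × 0.567 = 1.18. With sex almost balanced, the contrast actually varies with SD 0.417 around 0.6 − 0.045 = 0.555. (1.18 − 0.555) / 0.417 = 1.50, an upper tail of about 7%. Simulation, in which the estimated SE also varies, gives 8 to 9%.

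**4. Simulated power** (20,000 trials per scenario, realised 3/9 and 3/8 split, D = 2, r = 0.8, equal gains):

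| Comparison | Without sex | With sex |
|---|---|---|
| M1 | about 9% | 28% |
| Change | 58% | 58% |
| M1 adjusted for M0 | 59% | 60% |

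**5. What sex adds once M0 is in the model.**
- r of at least 0.8, equal gains: 0 to 2 points (at D = 2 and r = 0.9, 86% either way).
- r = 0.6, D of 2 to 3, equal gains: about 4 to 5 points.
- r = 0.8, D = 2, men gain 0.25 SD more: about 5 points.
- r = 0.8, D = 2, men gain 0.5 SD more: about 10 points (50% to about 60%), with mean CI width falling from 1.18 to 1.06.
- Gains proportional to level (10 to 20%): about 0 to 4 points.

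If change is compared and men gain 0.5 SD more, adding sex raises power from 52% to 58% (r = 0.8) or from about 78% to 86% (r = 0.9).

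**6. Cost if sex is irrelevant.** Without M0, the residual df fall from 21 to 20, the critical t rises from 2.080 to 2.086, and the variance factor is 1.0007. The CI is then (2.086 / 2.080) × √1.0007 = 1.003 times as wide. With M0 in the model, simulated power was 60.2% without sex and 59.8% with it; a repeat gave 60.8% and 60.1%.

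**7. Type I error of the unadjusted M1 test.** Given the realised split it is about 3.4%, 0.9% and 0.1% at D = 1, 2 and 3. When the 6 men and 17 women are re-randomised without stratification, it is 4.8 to 5.2%.

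**The case against.** A reader might infer that every between-group test here has intervals that are too wide and loses power because sex is ignored, and that a sex term cures this. The documents do not support that. If changes were compared, each person's stable level already cancels, and with equal gains there is nothing left for sex to explain. The text does not say which variable was used, so a loss of power is possible but not established. This objection stands.

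It is also fair to say that the striking drops in power belong to a raw M1 comparison and that M0 alone repairs nearly all of them. The larger gains from sex beyond M0 need a modest correlation or an extra male gain. An extra 0.5 SD in men would be almost as large as the assumed treatment effect, after only eight sessions (4 weeks, two per week). This stands too and sets the order of priority: M0 first, sex second.

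A reader might also infer that the unadjusted test is too conservative in general. That holds only conditional on the near-equal split that occurred. The protocol names a randomisation tool but states no stratification by sex, and over unstratified allocations the test keeps its nominal level.

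Finally, the sentence on metabolic response might be read as the plan's justification for leaving sex out of the analysis. It explains eligibility and makes no such claim.

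What the objections do not remove is that the listed between-group tests use neither recorded variable, and that including both costs very little.

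**Conclusion.** The point holds in a conditional form. The plan leaves the analysed variable open and uses neither M0 nor sex between arms. If M1 is compared, the loss can be large: at D = 1, 2 and 3 the error variance is inflated by factors of 1.21, 1.84 and 2.90. If change is compared, the loss attributable to sex runs from none, with equal gains, to several points of power if men gain more. Every size depends on assumed values of D, r and the gains.

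This is a worthwhile, low-cost improvement and does not show that the reported comparison is wrong. Nor would it make the trial well powered. Even with the sex difference fully removed, an M1 comparison of 12 vs 11 has about 45% power for a 0.8 SD effect and needs about 1.23 SD for 80%.

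**What to change.** In the Statistical Analysis section, name the analysed variable and make the between-group comparison of each of the four outcomes a linear model of M1 on group, M0 and sex. Report the adjusted group difference with its 95% CI. Enter sex as a main effect only; six men are too few to test a sex-by-group interaction.

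If a rank test is kept, make it a sensitivity analysis on change scores. Stratifying a rank test by sex is a weak substitute: the male stratum is 3 vs 3, where the smallest exact two-sided p-value is 2/20 = 0.10, and such a test on M1 would still not use M0.

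The text is in the past tense and reports the realised sex split. If outcome results have already been seen, label the adjusted model as added afterwards and show it beside the listed analysis.

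The cost is a sentence or two in the plan and a standard linear model in the named software, with no new data. The sex term uses one degree of freedom, about 0.5 to 1 point of power if sex turns out to be irrelevant.

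### Two exclusion criteria can be met only after training starts, one of them in the BFR arm only, and no all-randomised analysis set is stated, so the plan permits partly arm-specific removal after allocation; no bias is shown.

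*Combined protocol and SAP*

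**What the plan says.** Under Eligibility Criteria, most exclusion criteria describe a person's history or condition at entry. Two do not:

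- "Persistent symptoms during training: numbness, tingling, or pain >7/10 on a numeric rating scale (BFR group criterion", which is marked as applying to the BFR group;
- "Missing more than one training session", which carries no group label. Training Protocol gives the schedule: "The intervention lasted 4 weeks with two sessions per week".

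The BFR Application section gives a milder response at the same symptom threshold: "symptoms >7/10 prompted protocol adjustment or session cancellation".

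On outcome timing, Methods states: "Measurements were obtained at baseline (M0) and at least 24 h after the final training session (M1". Nothing is added about people who stop training early.

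Study Design reports "an experimental BFR group ($n = 12$; 3 men, 9 women" with no loss mentioned, and a high-load group of 11 described as "3 men, 8 women; one dropout". No reason is given for the dropout.

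Statistical Analysis names the between-group tests (Fisher's exact test, "the Mann-Whitney U test, or independent-samples t tests"), paired t tests within groups, effect-size bands and the significance level. It does not say who is included in the comparison or how a missing M1 value is handled.

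**The concern.** Randomisation makes the two arms comparable at allocation. That protection holds only if people are then analysed in the arm to which they were assigned. An exclusion criterion that depends on how someone tolerated or attended training acts after allocation, and what it selects on may be related to the response to training.

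The symptom criterion is the more serious of the two because it has no counterpart in the high-load arm. If the BFR participants who tolerated the cuff worst were removed while every high-load participant stayed, the BFR arm would become a selected group and the comparator would not. The attendance rule applies to both arms, but it would also turn an all-randomised comparison into a comparison of attenders. With about a dozen people per arm, one removal is a noticeable share of the data.

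**Working it through.** The plan states no figure on this point, so there is none to reproduce. The check reads the sections against each other and then sizes what the rule could do.

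**1. When the criteria can be met.** Training ran 4 weeks × 2 sessions = 8 sessions, so the second missed session meets the attendance criterion. The timing of randomisation is not given. However, a criterion labelled for the BFR group can apply only once a person is in that group, and no session can be missed before training begins. Both act after allocation.

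**2. Whether another section cancels them.** BFR Application covers a symptom rating above 7/10 in a session and responds by modifying or calling off that session. The exclusion list covers symptoms that persist. The two can be read together as steps, and the milder step does not delete the stricter one.

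**3. Whether an analysis set rescues them.** Statistical Analysis names no all-randomised, intention-to-treat or per-protocol set. Paired t tests need both M0 and M1, so anyone without M1 drops out of those tests by default.

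**4. What was reported.** BFR: 3 + 9 = 12. High load: 3 + 8 = 11, plus a mention of one dropout. That 12 were randomised to BFR is inferred from the absence of a reported loss. The document also leaves open whether the 11 in the high-load arm are those left after the dropout (12 randomised) or include it (11 randomised).

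**5. What the BFR-only rule could do (illustration).** One removal is 1/12 = 8.3% of the arm. The simulation assumed standard-normal responses, no true difference, 12 − k BFR against 11 high load, and a t test at 0.05 taken as two-sided (the plan does not state sidedness). It removed the k BFR participants at the worst end of a symptom score correlated rho with response, over 400,000 trials per case:

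| rho | k = 1 | k = 2 | k = 3 |
|---|---|---|---|
| 0 | no shift, 5.0% | no shift, 5.0% | no shift, 5.0% |
| 0.3 | 0.04 SD, 5.2% | 0.08 SD, 5.4% | 0.12 SD, 5.8% |
| 0.5 | 0.07 SD, 5.5% | 0.14 SD, 6.4% | 0.20 SD, 7.4% |

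Each cell gives the size of the shift in the BFR mean and the type I error. The shift favours BFR if those with the worst symptoms respond weakly, and goes against it if they respond strongly. Neither rho nor k comes from the document.

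**6. The one reported loss (generic missing-data sensitivity).** This step does not measure the arm-specific rule. Assume 12 were randomised to high load and the person lost was the weakest on a variable correlated rho with response. The high-load mean then rises by 0.045 SD at rho = 0.3, 0.074 at 0.5 and 0.147 at 1; losing the strongest gives about the same size in the other direction. As a check at rho = 1, the expected maximum of 12 standard normals is 1.629, and 1.629/11 = 0.148. The standard error of a 12 v 11 difference is √(1/12 + 1/11) = 0.417 SD, so the shifts are 0.045/0.417 = 0.11, 0.074/0.417 = 0.18 and 0.147/0.417 = 0.35 of one standard error.

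**7. A simple bound for that person.** Give the missing participant a value 2 SD from the mean m of the 11 measured. The new mean is (11m + m ± 2)/12 = m ± 2/12, a move of ±0.17 SD. If only 11 were randomised and 10 measured, it is ±2/11 = ±0.18 SD.

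**The case against.** The strongest reply is that nothing went wrong. No BFR participant is reported lost, the high-load loss is called a dropout and not an exclusion, and a symptom limit for cuff training is sound safety practice. Requiring attendance is also defensible in a small comparison of two training regimens, provided it is declared. All of this stands, and it limits the point to what the rules permit. It does not settle the point, because stopping the cuff is a different act from leaving the study, and no section says that those who stop are kept in the analysis.

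Four stronger readings are tempting, and the document does not support them:

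- *The BFR arm was selectively trimmed.* No BFR loss is reported. If 12 is the number randomised, the bias from BFR removals is zero.
- *The high-load dropout shows the rules at work.* The symptom rule could not apply to that person, and no reason links the loss to attendance. A voluntary withdrawal would give the same figures with neither rule in the plan, so the 0.04 to 0.15 SD range is a missing-data sensitivity, and its upper end needs rho = 1.
- *A session cancelled for symptoms counts as missed, so the attendance rule also falls harder on BFR.* The text does not say so. Someone whose session was cancelled for symptoms had attended, and changing the protocol was an alternative to cancelling. There is no basis for projecting exclusions from assumed cancellation rates.
- *The M1 wording means early stoppers were not measured.* It sets a minimum interval after training and is silent on early stoppers.

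**Conclusion.** The point holds as a fault in the stated rules. Two post-allocation events are grounds for exclusion from the study, one of them in a single arm, and no analysis set offsets them. The text supports this part with high confidence.

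No consequence is demonstrated. It is not known whether either rule was ever applied. The sizes in the working depend on assumed values for the number removed and for rho, and they disappear at rho = 0. Even under those assumptions, a single BFR removal raises type I error only to about 5.5% at rho = 0.5. This should be corrected because the correction is cheap and analysis as allocated is what the randomised comparison rests on. It is not a reason to discount the results.

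**What to change.** Take both items out of the exclusion list and restate them as rules for stopping training, keeping the BFR symptom limit for safety. State that meeting either rule does not end study participation, that M1 is obtained where possible, and that the main analysis includes all randomised participants in their assigned arm. An adherent set can be a secondary analysis.

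The document is written in the past tense, so conduct may be closed and new M1 visits may not be possible. In that case, what can still be done is:

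- include in the main analysis any excluded participant who has M1 data;
- report by arm the numbers randomised, withdrawn (with reasons) and analysed, including how many were randomised to each arm;
- add the ±2 SD bound for the high-load dropout and say whether the conclusion survives it.

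The cost is a few sentences, a participant-flow statement and one short sensitivity analysis. The statistical price is slight dilution of the estimated effect by people who did not complete training.

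### Symptoms, the response to them, and symptom-based removal are described for the BFR arm only, so tolerability of the two programs cannot be compared

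*Combined protocol and SAP*

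**What the plan says.** Under Training Protocol, the BFR Application paragraph states "Participants rated pain, tingling, and numbness on a" 0–10 scale, and that "symptoms >7/10 prompted protocol adjustment or session cancellation". Under Eligibility Criteria, the exclusion list includes "Persistent symptoms during training: numbness, tingling, or pain >7/10 on a numeric rating scale (BFR group criterion").

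The comparator paragraph opens "High-load strength training group: Training followed ACSM hypertrophy guidelines at 70% 1RM" and goes on to sets, repetitions, rests and tempo. It describes no symptom rating and no symptom rule.

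Study Design gives "an experimental BFR group ($n = 12$; 3 men, 9 women") and "an active comparator high-load group ($n = 11$; 3 men, 8 women; one dropout"). No reason or timing is given for the dropout. Statistical Analysis plans no summary of the symptom ratings, of sessions changed because of symptoms, or of withdrawals.

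**The concern.** A harm that is asked about in one arm only will tend to be found in that arm only. Pain is not specific to the cuff: both arms load the shoulder with the same three exercises, and the eligibility criteria exclude people who already have shoulder pain. If the ratings are reported, BFR will look less well tolerated because only BFR participants were asked. If they are not reported, the trial says nothing on the matter.

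The exclusion criterion adds a second asymmetry. It refers to symptoms during training, so it can act only after randomization, and it acts in one arm. It could remove BFR participants who tolerate the program poorly, with no counterpart in the high-load arm, and Statistical Analysis names no analysis population that would say how they are handled.

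**Working it through.** The documents give no symptom rate, event count or sample-size figure on this point, so there is nothing to reproduce. The check is mainly a comparison of passages, followed by two small calculations.

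**1. Is the rating really confined to one arm?**
- The rating and the response above 7/10 stand in BFR Application, next to cuff placement and pressure.
- The exclusion criterion carries an explicit arm label, so the restriction is stated and does not rest on the placement of a sentence alone.
- In the same part of the protocol, session length is expressly given for both groups. The rating has no such marking.
- The high-load paragraph contains load, sets, repetitions, rests and tempo only.

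**2. Do the two symptom rules agree?**
- Eligibility Criteria: persistent symptoms above 7/10 are listed as an exclusion. What counts as persistent is not defined.
- BFR Application: symptoms above 7/10 lead to a changed protocol or a cancelled session.
- The text does not say when the second becomes the first, or whether a cancelled session counts toward the separate criterion on missed sessions.

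**3. What does the dropout show?** Inputs: 12 BFR participants with no dropout mentioned; 11 high-load participants and one dropout. The text does not say whether the 11 includes that person.
- If 11 remained out of 12: 0/12 vs 1/12. The single event falls in either arm with probability 12/24 = 0.5. Both outcomes are equally likely and both count, so two-sided Fisher p = 1.00. The rate 1/12 = 8.3% has an exact 95% interval of 0.2% to 38.5%.
- If 11 were randomized: 0/12 vs 1/11. The probability that the event falls in the high-load arm is 11/23 = 0.478. The other outcome, 12/23 = 0.522, is more likely and is not counted, so p = 0.48. The rate 1/11 = 9.1% has an interval of 0.2% to 41.3%.
- For 0/12, the upper 95% limit is 1 − 0.025^(1/12) = 26.5%.

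**4. What would equal rating allow at 12 vs 11?**
- With 0/11 high-load participants above the threshold, at least 5/12 in the BFR arm are needed for p < 0.05: [C(12,5) + C(11,5)] / C(23,5) = (792 + 462)/33,649 = 0.037. With 1/11, at least 7/12 are needed (p = 0.027).
- Exact power of Fisher's test under assumed true rates (BFR vs high-load; the documents give none): 17% for 30% vs 5%, 45% for 50% vs 10%, 66% for 60% vs 10%.
- Chance of seeing at least one event among 11 fully rated people, 1 − (1 − p)^11: 43%, 69% and 91% for assumed rates of 5%, 10% and 20%.

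Equal rating would therefore give a fair description, not a useful test.

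**The case against.** The strongest reply is that the rating is an operating check on the cuff and not an outcome. The objectives are strength, power, endurance and hypertrophy; the four assessments match them, and no tolerability analysis is planned. This stands: no planned comparison is affected. It does not remove the asymmetry in whatever is later said about symptoms or removals.

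Several stronger readings are tempting, and the documents do not support them:
- *Injury in the high-load arm went unmonitored.* The documents are silent on adverse-event and injury recording in both arms. The BFR rating covers symptoms, not injury, and Methods mentions safety protocols for the research team without tying them to an arm. What can be said is that no such recording is described.
- *The dropout points to poor tolerability of high-load training.* No reason is stated, and the counts carry no information on this.
- *About half of the training sessions lacked symptom ratings.* Eight sessions each give 88/184 = 47.8%, but this is only the comparator's share of participants (11/23). It measures no effect on any estimate, and the text does not state how often BFR participants were rated.
- *The efficacy comparison is biased by one-sided removal.* The criterion makes this possible, but the documents report no symptom-based removal.

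Finally, the text is in the past tense with arm sizes known. Ratings may no longer be obtainable in the high-load arm, and then only the reporting part of the fix remains.

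**Conclusion.** The point holds in a limited form. Symptom rating, the response above 7/10 and the symptom-based removal criterion are described for the BFR arm only, and no adverse-event recording is described for either arm. Tolerability cannot be compared from data collected this way, and any symptom report would be one-sided by construction. The two stated consequences of symptoms above 7/10 also need to be reconciled.

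The gap is worth closing because it is cheap to close, but it does not undermine the stated objectives. Its size cannot be put as a bias in any estimate, since the documents give no symptom data. The conclusion assumes that the documents describe the procedures fully. If symptoms were in fact recorded in the high-load arm, saying so and reporting them on the same footing would answer most of it.

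**What to change.** - Move the 0–10 rating of pain, tingling and numbness from BFR Application to Training Protocol, recorded in both arms at the same points in each session. The action taken in each arm remains for the investigators to set.
- Add to Statistical Analysis a descriptive table by arm: participants and sessions with a reading above 7/10, sessions adjusted or cancelled, and every removal or withdrawal with its reason and timing, including the one dropout.
- Reconcile the exclusion criterion for persistent symptoms with the response given under BFR Application.
- If data collection is complete, state what was recorded in each arm, report symptom-based removals by arm, and make no comparative tolerability or safety claim.

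Cost: if sessions are still to be run, about a minute per high-load session (an estimate; the documents give none) for staff already present, more symptom reports to review, and one table. If they are finished, only the table and the accompanying statements. At 12 vs 11 the comparison remains descriptive.
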